5.7 Subject Discontinuation

Subjects will receive study treatment until treatment discontinuation for one of the reasons listed below. However, subjects may discontinue study treatment or withdraw their consent to participate in the study at any time without prejudice. All reasons for discontinuation or withdrawal from trial will be recorded.

The maximum duration of treatment for pembrolizumab will be up to 35 cycles. The duration of treatment for XELOX will be until unacceptable drug-related toxicity or disease progression. If capecitabine is not tolerated, monotherapy with pembrolizumab may be continued. Patients who complete 35 cycles of therapy and have complete response or prolonged stable disease may also elect to end therapy with capecitabine after a discussion with their treating physician and with approval of the PI. Re-introduction of oxaliplatin is permitted provided that neuropathy has improved. Reasons for subject discontinuation by the Investigator may include, but are not limited to, the following:

- Death
- Confirmed radiographic disease progression (Note: With approval of the Lead PI, a subject may be granted an exception to continue on study treatment with confirmed radiographic progression if clinically stable or clinically improved.)
- Significant noncompliance by subject or Investigator
- Investigator or Lead PI determination that it is no longer safe and/or no longer in the subject's best interest to continue participation
- Withdrawal of consent
- Lost to follow-up
- Necessity for treatment with other anticancer treatment prohibited by protocol
- Sexually active subjects who refuse to use medically accepted methods of contraception during the course of the study and for 120 days following the last dose of study drug
- Women who become pregnant or are breast feeding
- Request by regulatory agencies for termination of treatment of an individual subject or all subjects under the protocol
- The following **Treatment-Related Discontinuation Criteria** attributed to pembrolizumab:
 - Any Grade 2 uveitis, eye pain, or blurred vision that does not respond to topical therapy and does not improve to Grade 1 OR requires systemic treatment.
 - Recurrent Grade 2 pneumonitis
 - Any Grade 3 non-skin adverse event lasting > 7 days, with the following exceptions for treatment-related laboratory abnormalities, uveitis, pneumonitis, bronchospasm, diarrhea, colitis, neurologic toxicity, hypersensitivity reactions, and infusion reactions:
 - Grade 3 uveitis, pneumonitis, bronchospasm, diarrhea, colitis, neurologic toxicity, hypersensitivity reaction, or infusion reaction of *any duration* requires discontinuation
 - Grade 3 laboratory abnormalities do not require treatment discontinuation except Grade 3 thrombocytopenia > 7 days OR associated with bleeding requires discontinuation
 - Any liver function test (LFT) abnormality that meets the following criteria:

- AST or ALT > 8 x ULN
- Total bilirubin > 5 x ULN
- Concurrent AST or ALT > 3 x ULN and total bilirubin > 2 x ULN
- Any Grade 4 adverse event or laboratory abnormality, except for the following events:
 - Grade 4 amylase or lipase abnormalities that are not associated with symptoms or clinical manifestations, or radiographic signs of pancreatitis
 - Isolated Grade 4 electrolyte imbalances/abnormalities that are not associated with clinical sequelae and are corrected with supplementation/appropriate management within 3 days of their onset
 - Grade 4 endocrinopathy adverse events such as adrenal insufficiency, ACTH deficiency, hyper- or hypothyroidosis, or glucose intolerance, which resolve or are adequately controlled with physiologic hormone replacement (steroids, thyroid hormones) or glucose controlling agents, respectively, retreatment can be considered
- Any dosing interruption lasting > 6 weeks with the following exceptions:
 - Dosing interruptions to allow for prolonged steroid tapers to manage treatment-related adverse events are allowed
 - Dosing interruptions > 6 weeks that occur for non-treatment-related reasons may be allowed
- Any adverse event, laboratory abnormality, or intercurrent illness which, in the judgment of the Investigator, presents a substantial clinical risk to the subject with continued pembrolizumab or lanreotide depot dosing

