Immune-related AEs	Toxicity grade or conditions (CTCAEv4.0)	Action taken to pembrolizumab	irAE management with corticosteroid and/or other therapies	Monitor and follow-up
Hypothyroidism	Grade 2	Continue	Initiate thyroid replacement hormones (eg, levothyroxine or liothyroinine) per standard of care	
 Monitor for signs and symptoms of thyroid disorders.
Nephritis and Renal dysfunction	Grade 2	Withhold	Administer corticosteroids (prednisone 1-2 mg/kg or equivalent) followed by taper.	
 Monitor changes of renal function
	Grade 3 or 4	Permanently discontinue		
Myocarditis	Grade 1 or 2	Withhold	Based on severity of AE administer corticosteroids	
 Ensure adequate evaluation to confirm etiology and/or exclude other causes
	Grade 3 or 4	Permanently discontinue		
All other immune-related AEs	Intolerable/persistent Grade 2	Withhold	Based on type and severity of AE administer corticosteroids	
 Ensure adequate evaluation to confirm etiology and/or exclude other causes
	Grade 3	Withhold or discontinue based on the type of event. Events that require discontinuation include and not limited to: Gullain-Barre Syndrome, encephalitis		
	Grade 4 or recurrent Grade 3	Permanently discontinue		

¹Withhold or permanently discontinue pembrolizumab at the discretion of the investigator or treating physician.

NOTE: For participants with Grade 3 or 4 immune-related endocrinopathy where withhold of pembrolizumab is required, pembrolizumab may be resumed when AE resolves to ≤Grade 2 and is controlled with hormonal replacement therapy or achieved metabolic control (in case of T1DM).

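### Section 5.7 lists a clinical Grade 3 endocrinopathy lasting more than 7 days as a reason to stop pembrolizumab but exempts a controlled Grade 4 one; Table 7.1.1 permits resumption after either where dosing is withheld, and no text says which governs

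*Combined protocol and SAP*

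**What the plan says.** Section 5.7 opens with "Subjects will receive study treatment until treatment discontinuation for one of the reasons listed below". Its list is then introduced more softly: "Reasons for subject discontinuation by the Investigator may include, but are not limited to, the following".

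Under the heading for treatment-related criteria attributed to pembrolizumab, the Grade 3 item reads "Any Grade 3 non-skin adverse event lasting > 7 days, with the following exceptions". The exceptions begin with laboratory abnormalities, uveitis and pneumonitis, and continue with "bronchospasm, diarrhea, colitis, neurologic toxicity, hypersensitivity reactions, and infusion reactions". No endocrine event is named. The laboratory exception is spelled out as "Grade 3 laboratory abnormalities do not require treatment discontinuation except Grade 3 thrombocytopenia > 7 days", or thrombocytopenia with bleeding.

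The Grade 4 item makes any Grade 4 event a criterion, apart from named exceptions. One of these is "Grade 4 endocrinopathy adverse events such as adrenal insufficiency, ACTH deficiency, hyper- or hypothyroidosis, or glucose intolerance, which resolve or are adequately controlled" with hormone replacement or glucose-controlling agents; for these the section says that retreatment can be considered.

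Table 7.1.1 (Section 7.1.1) does not separate Grades 3 and 4 in its endocrine rows:
- **New-onset type 1 diabetes, or Grade 3 or 4 hyperglycemia with evidence of beta-cell failure:** withhold.
- **Grade 3 or 4 hypophysitis or hyperthyroidism:** withhold or stop permanently, at the physician's discretion (footnote 1).
- **Hypothyroidism:** a Grade 2 row only.
- **Adrenal insufficiency:** no row of its own.

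For Grade 3 or 4 endocrinopathy where withholding is required, the NOTE under the table says "pembrolizumab may be resumed when AE resolves to ≤Grade 2 and is controlled with hormonal replacement therapy", or once metabolic control is achieved in type 1 diabetes. Section 7.1 ends study treatment when pembrolizumab is permanently discontinued.

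**The concern.** Two things do not fit together. Within Section 5.7, a Grade 3 endocrine event of sufficient duration meets a stopping criterion, while a Grade 4 event of the same kind, once controlled, does not. The documents give no reason for treating the lower grade more strictly. Between sections, the table and its NOTE treat Grades 3 and 4 alike and allow a return to treatment that Section 5.7 does not provide for at Grade 3.

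The patient at issue has a clinical endocrine event that remains Grade 3 past day 7 and is later controlled. One investigator, reading Section 5.7, would take that patient off pembrolizumab and so, under Section 7.1, off all three drugs. Another, reading the table, could withhold and resume. Sites could therefore differ in treatment, in the recorded reason for discontinuation, and in the censoring date for the secondary PFS analysis in Section 9.1.1, which censors at removal from treatment. Tolerability is a secondary objective, so the recorded reasons matter too.

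**Working it through.** The main check is a comparison of rules; the plan states no figure on this point to reproduce.

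| Event | Section 5.7 | Table 7.1.1 and NOTE | Result |
|---|---|---|---|
| Grade 3 finding that is only a laboratory abnormality | Exempt | Not stricter for events with a row | No conflict from the 7-day rule |
| Clinical Grade 3, at Grade 2 or below within 7 days and controlled | Criterion not met | If withheld, may resume | No conflict |
| Clinical Grade 3, still Grade 3 after 7 days, later controlled (new-onset type 1 diabetes, hypophysitis, hyperthyroidism) | Criterion met | Withhold, or withhold/stop at discretion; if withheld, may resume | Listed stop against permitted resumption |
| Grade 4, controlled, with its own row | Exempt; retreatment can be considered | If withheld, may resume | Compatible |
| Grade 4, controlled, no row (e.g. adrenal insufficiency) | Exempt | If it falls in the row for all other immune-related events: permanent discontinuation | Conflict in the other direction |

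The third and fourth rows show the inversion within Section 5.7. The third also shows the conflict between sections. In the fifth, the NOTE does not help, because it applies only where withholding is the required action.

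**Does any text settle it?** Section 7.1.1 gives the table precedence only over its own note on recurrent Grade 3 and life-threatening toxicity. Section 7.1 allows other dose modifications in the interest of a subject's safety, but does not say that a discontinuation criterion, once met, may be set aside. Section 7.2.5 covers Grade 2 to 4 hypothyroidism with replacement therapy and says nothing about pembrolizumab dosing. None ranks Section 5.7 against the table.

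**How often could it arise?** The inputs are 17 hypophysitis cases of any grade (Table 1.2.1.3.1), 2799 subjects (Table 1.2.1.3.2, same reference safety dataset) and 35 planned patients (Section 9.1).

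- Rate: 17 / 2799 = 0.00607, or 0.6%.
- Chance of at least one case of any grade: 1 − (1 − 17/2799)^35 = 0.19.
- The documents give no split by grade or duration. If, as an assumption, 25% of cases were clinical Grade 3 lasting more than 7 days: 1 − (1 − 0.25 × 17/2799)^35 = 0.05.
- If 50% were: 1 − (1 − 0.50 × 17/2799)^35 = 0.10.

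Thus 19% is a ceiling for hypophysitis, and 5% to 10% illustrates what qualifying cases might look like. Thyroid events, diabetes and other endocrine events would add to this; the 19% is not a ceiling for all endocrine events together.

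**The case against.** The strongest reply is that the two sections can be read together. Section 5.7 never says that the Grade 3 stop is permanent, and its list is introduced as reasons that may apply. For hypophysitis and hyperthyroidism the table itself allows permanent discontinuation, so an investigator who stops satisfies both sections.

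Much of this stands. A reader might infer that Section 5.7 permanently stops the drug while the table orders it resumed, so that the two give opposite instructions. The documents do not support that: the table permits resumption and never requires it. A reader might also infer that the table lets every Grade 3 or 4 endocrinopathy resume. It does not. The NOTE is conditional on withholding, adrenal insufficiency has no row, and hypothyroidism has none above Grade 2.

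The reply does not remove the point. The opening sentence of Section 5.7 runs treatment until a listed reason occurs, the items are headed as criteria, and detailed exceptions would serve little purpose if the list were wholly optional. The inversion between Grades 3 and 4 lies inside Section 5.7 and does not depend on how the table is read.

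It can also be said that the effect on the analysis is slight. That is right for the primary analysis, in which patients removed for unacceptable toxicity are still followed for PFS.

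**Conclusion.** The inconsistency is real but narrow. Section 5.7 is stricter for a clinical endocrinopathy that stays Grade 3 for more than 7 days than for a controlled Grade 4 one. At Grade 3 it lists a stop where Table 7.1.1 permits resumption. For endocrinopathies without a row, the two may also conflict at Grade 4, with the table the stricter.

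This rests on three readings: that the 7 days count time at Grade 3, that purely laboratory findings are exempt, and that events without a row fall in the row for all other immune-related events.

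The size is likely small. A reader might take 19% as the chance that the conflict arises. It is only an upper bound for qualifying hypophysitis, and it assumes that the reference dataset's rate carries over to this combination regimen. For an affected patient the consequence can be the loss of all study treatment. For the analysis, the secondary PFS censoring date and the recorded reason for discontinuation can change; primary PFS follow-up is unaffected.

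**What to change.** Reconcile four pieces of text so that one consistent rule covers Grade 3 and Grade 4 endocrinopathy:

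1. the Section 5.7 criterion for Grade 3 events lasting more than 7 days;
2. the Section 5.7 exception for Grade 4 endocrinopathy;
3. the endocrine rows of Table 7.1.1 and the NOTE;
4. the handling of endocrinopathies without a row at the relevant grade, including adrenal insufficiency and hypothyroidism above Grade 2.

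State which passage governs if they differ. The sponsor's clinicians decide which rule stands; this review takes no position on that.

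The cost is a protocol wording change, with no added visits, tests or sample size.

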6.5.2 Prohibited Concomitant Medications

Subjects are prohibited from receiving the following therapies during the Screening and Treatment Period of this study:

- Antineoplastic systemic chemotherapy or biological therapy
- Immunotherapy not specified in this protocol
- Chemotherapy not specified in this protocol
- Investigational agents other than pembrolizumab
- Radiation therapy to target lesions. If subject needs palliative local radiation (e.g., for relief of dysphagia or of pain from bony metastases), protocol therapy may be delayed with the

approval of the lead PI. Radiation therapy must be completed for at least 14 days prior to resumption of protocol treatment.

- Live vaccines within 30 days prior to the first dose of study drug and while participating in the study. Examples of live vaccines include, but are not limited to, the following: measles, mumps, rubella, varicella/zoster, yellow fever, rabies, BCG, and typhoid vaccine.
- Systemic glucocorticoids for any purpose other than to modulate symptoms from an event of clinical interest of suspected immunologic etiology. Prophylactic dosing of steroids prior to treatment and administration of low dose steroids for up to 48 hours post treatment is permitted. Corticosteroids administered as pre-medication for IV contrast allergy are also allowed.

Subjects who, in the assessment by the Investigator, require the use of any of the aforementioned treatments for clinical management should be removed from the trial. Subjects may receive other medications that the Investigator deems to be medically necessary.

There are no prohibited therapies during the Follow-up Period.

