7.1 Dose Modifications

Subjects experiencing one or more AEs due to the study drug(s) may require dose modification(s) as described in [Section 7.1.1](#) and [Section 7.1.2](#). At the discretion of the Investigator, dose modifications are permitted outside of the those provided in the protocol if the Investigator feels it is in the interest of the subject's safety (e.g., due to multiple toxicities, persistent toxicities, intercurrent illness, or short term compliance or monitoring issues, etc.).

Subjects may need to be followed at least weekly when any study drug is held for toxicity until the toxicity returns to Grade ≤ 1 or is determined to be chronic or irreversible.

Dosing interruptions are permitted in the case of medical / surgical events or logistical reasons not related to study therapy (e.g., elective surgery, unrelated medical events, patient vacation, and/or holidays). Subjects should be placed back on study therapy within 4 weeks of the scheduled interruption, unless otherwise discussed with the Lead PI. The reason for interruption should be documented in the patient's study record. Dosing may be interrupted if there is a need for local palliative radiation therapy, with the approval of the lead PI. In this case, protocol-based therapy cannot be resumed until patients are at least 14 days out from the end of radiation.

If pembrolizumab is permanently discontinued, the subject will be discontinued from study treatment. Maximum duration of treatment for pembrolizumab will be up to 35 cycles. If patients discontinue oxaliplatin due to intolerance, they can be maintained on capecitabine and pembrolizumab. If capecitabine is not tolerated, pembrolizumab monotherapy may be continued. Re-introduction of oxaliplatin is permitted provided neuropathy has improved.

All dose modifications and reasons for modification must be recorded in the CRF.

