7.1.1 Pembrolizumab Dose Modifications

Adverse events (both non-serious and serious) associated with pembrolizumab exposure may represent an immunologic etiology. These adverse events may occur shortly after the first dose or several months after the last dose of treatment.

Pembrolizumab must be withheld for treatment-related toxicities as per Table 7.1.1. There are no dose reductions for pembrolizumab.

Note: Subject must be permanently discontinued for any severe or Grade 3 treatment-related toxicity that recurs or any life-threatening event unless otherwise specified in Table 7.1.1.

General Instructions:

1. Corticosteroid taper should be initiated upon AE improving to Grade 1 or less and continue to taper over at least 4 weeks.
2. For situations where pembrolizumab has been withheld, pembrolizumab can be resumed after AE has been reduced to Grade 1 or 0 and corticosteroid has been tapered. Pembrolizumab should be permanently discontinued if AE does not resolve within 12 weeks of last dose or corticosteroids cannot be reduced to ≤ 10 mg prednisone or equivalent per day within 12 weeks.
3. For severe and life-threatening irAEs, IV corticosteroid should be initiated first followed by oral steroid. Other immunosuppressive treatment should be initiated first followed by oral steroid. Other immunosuppressive treatment should be initiated if irAEs cannot be controlled by corticosteroids.

Table 7.1.1 Pembrolizumab Dose Modifications

Immune-related AEs	Toxicity grade or conditions (CTCAEv4.0)	Action taken to pembrolizumab	irAE management with corticosteroid and/or other therapies	Monitor and follow-up
Pneumonitis	Grade 2	Withhold	
 • Administer corticosteroids (initial dose of 1-2 mg/kg prednisone or equivalent) followed by taper 	
 • Monitor participants for signs and symptoms of pneumonitis • Evaluate participants with suspected pneumonitis with radiographic imaging and initiate corticosteroid treatment • Add prophylactic antibiotics for opportunistic infections
	Grade 3 or 4, or recurrent Grade 2	Permanently discontinue		

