Diarrhea / Colitis	Grade 2 or 3	Withhold	
 • Administer corticosteroids (initial dose of 1-2 mg/kg prednisone or equivalent) followed by taper 	
 • Monitor participants for signs and symptoms of enterocolitis (ie, diarrhea, abdominal pain, blood or mucus in stool with or without fever) and of bowel perforation
	Grade 4	Permanently discontinue		

Immune-related AEs	Toxicity grade or conditions (CTCAEv4.0)	Action taken to pembrolizumab	irAE management with corticosteroid and/or other therapies	Monitor and follow-up
				
(ie, peritoneal signs and ileus).
 
 Participants with \geq Grade 2 diarrhea suspecting colitis should consider GI consultation and performing endoscopy to rule out colitis. Participants with diarrhea/colitis should be advised to drink liberal quantities of clear fluids. If sufficient oral fluid intake is not feasible, fluid and electrolytes should be substituted via IV infusion.
AST / ALT elevation or Increased bilirubin	Grade 2	Withhold	Administer corticosteroids (initial dose of 0.5- 1 mg/kg prednisone or equivalent) followed by taper	Monitor with liver function tests (consider weekly or more frequently until liver enzyme value returned to baseline or is stable)
	Grade 3 or 4	Permanently discontinue	Administer corticosteroids (initial dose of 1-2 mg/kg prednisone or equivalent) followed by taper	
Type 1 diabetes mellitus (T1DM) or Hyperglycemia	Newly onset T1DM or Grade 3 or 4 hyperglycemia associated with evidence of β -cell failure	Withhold	
 Initiate insulin replacement therapy for participants with T1DM Administer anti-hyperglycemic in participants with hyperglycemia 	
 Monitor participants for hyperglycemia or other signs and symptoms of diabetes.
Hypophysitis	Grade 2	Withhold	
 Administer corticosteroids and initiate hormonal replacements as clinically indicated. 	
 Monitor for signs and symptoms of hypophysitis (including hypopituitarism and adrenal insufficiency)
	Grade 3 or 4	Withhold or permanently discontinue ¹		
Hyperthyroidism	Grade 2	Continue	Treat with non-selective beta-blockers (eg, propranolol) or thionamides as appropriate	
 Monitor for signs and symptoms of thyroid disorders.
	Grade 3 or 4	Withhold or permanently discontinue ¹		

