10.3 Events of Clinical Interest

Select (non-serious and serious) adverse events called Events of Clinical Interest (ECI) that occur from the date of the first dose of study drug through 30 days following the last dose of study drug, must be recorded on the CRF and must be reported within 2 working days to Merck Global Safety.

An ECI for this study is any hepatic toxicity that is \geq Grade 2 or any grade resulting in dose modification or use of systemic steroids to the adverse event. Such adverse events include but are not limited to; hepatitis, autoimmune hepatitis, and transaminase elevations (ALT and/or AST).

Any overdose of pembrolizumab (1,000 mg or greater) is also considered an ECI for this study and should be reported as such, regardless of the outcome.

ECI Reporting Procedure:

Immediately upon awareness of an ECI, the Investigator (or designee) completes the **DCI SAE Report Form** and will submit the form within 2 business days of knowledge of the event to the funding company. External sites should submit the form within 24 hours to the Duke study team via the REDCap SAE reporting tool.

Note: It is imperative that initial ECI reports are submitted as soon as possible (within 2 business days of knowledge of the event) with available information to the supporting company. Missing and/or clarified event information may be provided in a follow-up report.

Follow-up information including severity, action taken, concomitant medications, and outcome should be communicated to the funding company as soon as possible using the same form mentioned above.

The Lead PI will review the report form with accompanying source document, sign page 5, and the PI or designee will then promptly submit it to the funding company.

Within two business days of receipt, the study team will also submit the SAE report form and other relevant safety information to the following supporting company:

Merck Global Safety
ATTN: Worldwide Product Safety
[contact]

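### A first Grade 3 diarrhea or colitis attributed to pembrolizumab is a mandatory stop in section 5.7 but a hold in Table 7.1.1, and the protocol does not say which prevails

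*Combined protocol and SAP*

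**What the plan says.** Section 5.7 opens its list with permissive wording: "Reasons for subject discontinuation by the Investigator may include, but are not limited to, the following". Within that list is a set of criteria attributed to pembrolizumab. One of them stops treatment for a Grade 3 non-skin event beyond 7 days and names diarrhea and colitis among its exceptions. The exception is then made stricter: "Grade 3 uveitis, pneumonitis, bronchospasm, diarrhea, colitis, neurologic toxicity, hypersensitivity reaction, or infusion reaction of" any duration requires discontinuation.

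Section 7.1.1 says pembrolizumab must be withheld as its table directs. The table row reads "Diarrhea / Colitis Grade 2 or 3 Withhold", and the next row reserves permanent discontinuation for Grade 4. Dosing can resume once the event is Grade 0 or 1 and the steroid has been tapered. A note adds that, unless the table specifies otherwise, subjects must be "permanently discontinued for any severe or Grade 3 treatment-related toxicity that recurs".

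Section 7.1 gives the consequence: "If pembrolizumab is permanently discontinued, the subject will be discontinued from study treatment".

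On steroids, section 6.5.2 prohibits "Systemic glucocorticoids for any purpose other than to modulate symptoms from an event of clinical interest of suspected immunologic etiology", apart from prophylactic use around dosing and contrast premedication. It adds that subjects who "require the use of any of the aforementioned treatments for clinical management should be removed from the trial". Section 10.3 begins its definition with "An ECI for this study is any hepatic toxicity" and adds only pembrolizumab overdose.

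**The concern.** Two sections that a site would consult for the same patient give different instructions, and the decision cannot be undone. Under 5.7 a patient with a first Grade 3 colitis comes off pembrolizumab, and therefore off oxaliplatin and capecitabine as study treatment. Under Table 7.1.1 the same patient is held, treated with steroids and may return to the full regimen.

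These are first-line metastatic patients, and the dose expansion cohort enrolls at external sites as well as the coordinating center (section 3.3). Two sites could each follow the protocol and manage identical patients differently. Tolerability is a secondary objective, so the count of discontinuations would partly reflect which page was read.

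**Working it through.** No figure in the plan needs reproducing here. The check is a comparison of the two sections for events attributed to pembrolizumab.

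| Event | Section 5.7 | Section 7.1.1 and its table | Result |
|---|---|---|---|
| First Grade 3 diarrhea/colitis | Stop, any duration | Withhold; may resume at Grade 0–1 after taper | Conflict |
| Recurrent Grade 3 diarrhea/colitis | Stop | Note says stop, but yields to the table, whose Grade 3 row says withhold | Probably the same, not explicit |
| Grade 4 diarrhea/colitis | Stop (Grade 4 rule) | Stop | Agree |
| Grade 3 pneumonitis | Stop, any duration | Stop | Agree |
| Grade 3 AST, ALT or bilirubin | Grade 3 laboratory values alone do not require a stop; stop at AST or ALT > 8 x ULN, bilirubin > 5 x ULN, or AST or ALT > 3 x with bilirubin > 2 x ULN | Stop at Grade 3 | Different criteria |

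**Is there a tie-break?**
- The phrase deferring to Table 7.1.1 qualifies only the note in 7.1.1. It does not reach 5.7.
- Section 7.2.2 gives steroid and taper guidance for Grade 3–4 diarrhea/colitis without saying whether to stop. Section 7.2.1, by contrast, does say to stop at Grade 3–4 pneumonitis. That contrast fits the table better than 5.7, but it is not a precedence rule.
- Section 5.7 also mentions lanreotide, which is not a study drug here. This hints that the list was carried over from elsewhere; it does not prove it.

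**Which results depend on the choice?** Section 9.1.1 follows patients for PFS after removal for toxicity in the primary analysis and, in a secondary analysis, censors them at removal. The secondary analysis and the discontinuation counts therefore depend on the rule followed. Primary PFS is largely unaffected. The qualification is needed because 9.1.1 describes this follow-up for patients with at least one on-treatment restaging or earlier unequivocal progression, and a patient stopped before the first restaging is not plainly covered.

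**How many patients?** Section 1.2.1.3 gives reference-dataset frequencies of 48/2799 = 1.7% for colitis and 625/2799 = 22.3% for diarrhea. Neither is broken down by grade, and neither comes from this combination. They do not give the rate of a first Grade 3 event attributed to pembrolizumab, so no expected count among 35 patients follows from them.

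**Steroid wording.** Section 6.5.2 ties its therapeutic exception to an event of clinical interest. Section 10.3 limits that term to hepatic toxicity and overdose, while Table 7.1.1 directs steroids for pneumonitis, colitis, hypophysitis and nephritis as well. The term in 6.5.2 is too narrow.

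**The case against.** The best defense is that the two rules can be reconciled. The table makes withholding mandatory but resumption only possible, so a site that withholds and then stops under 5.7 breaches no mandatory sentence. The lead-in to 5.7 is permissive, and section 7.1 lets investigators modify dosing outside the protocol's provisions for a subject's safety.

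Part of this stands: a cautious site has a defensible route. It does not remove the conflict. The table keeps permanent discontinuation for Grade 4, so a site that holds and resumes is also following the protocol. The line in 5.7 is itself mandatory despite the permissive lead-in. Safety discretion does not set a default.

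It can also be said that letting the table govern picks the less restrictive rule without evidence that the sponsor intended it. That is fair. The documents do not settle intent, and the essential requirement is one action in both places.

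Four stronger readings are tempting and are not supported:

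- *Every Grade 3 diarrhea triggers the conflict.* It does not. The 5.7 criteria concern events attributed to pembrolizumab; section 7.1.2 has its own hold-and-reduce rules for XELOX.
- *Section 6.5.2 expels patients given steroids for non-hepatic immune events.* Taken literally it might, but other text shows this is not meant. Section 6.5 says only that discontinuation may be needed, 6.5.1 allows treatment necessary for the subject's welfare, 5.7 allows interruptions for prolonged steroid tapers, and 7.1.1 allows resumption after taper.
- *The 6-week limit in 5.7 contradicts the 12-week limit in 7.1.1.* The triggers differ: one is length of interruption, the other resolution of the event or steroid reduction. Prolonged steroid tapers are exempt from the first, and applying the stricter limit satisfies both.
- *The primary result is compromised.* Section 9.1.1 keeps following patients removed for toxicity.

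**Conclusion.** The point holds as an internal inconsistency in a stopping rule and should be fixed. For a first Grade 3 diarrhea or colitis attributed to pembrolizumab, the protocol gives two different actions, ranks neither, and attaches loss of all study treatment to one of them. A related mismatch exists for Grade 3 AST, ALT and bilirubin. Its extent depends on the CTCAE grade limits, which the protocol cites but does not reproduce.

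The consequence is for patient management, discontinuation counts and the secondary PFS analysis. No sample size, power or alpha figure changes. The size in patients is unknown because the documents give no rate for the event; any probability of seeing a case among 35 would rest wholly on an assumed rate. The 6.5.2 wording is a minor terminology correction and adds nothing to the severity.

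**What to change.** 1. In 5.7, state that Table 7.1.1 governs any event it lists by name. Limiting this to named events stops the table's catch-all row from displacing 5.7's rules on, for example, uveitis. The sentence also settles Grade 3 AST, ALT and bilirubin.
2. In 5.7, remove diarrhea and colitis from the any-duration line, but keep them as exceptions to the rule on Grade 3 events beyond 7 days. Otherwise that rule would bring the conflict back for longer events.
3. Add recurrent Grade 3 to the stop row for diarrhea/colitis in Table 7.1.1, so that the 7.1.1 note is explicit there. The result is: first Grade 3, withhold; recurrent Grade 3 or Grade 4, stop.
4. In 6.5.2, replace the term event of clinical interest with immune-related adverse event managed under 7.1.1 or 7.2.

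If the sponsor prefers the stricter rule, the table should instead be changed to stop at Grade 3. Either way, both places must say the same thing.

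The cost is wording in 5.7, Table 7.1.1 and 6.5.2, the IRB approval that section 11.2 requires for a revision, and a memo to sites. No visits or patients are added.
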